That is why we decided to study the role of Sildenafil Citrate in expectant and conservative management of mild pre-eclampsia, as it has shown its ability to be beneficial to both the mother and the fetus through increasing the maternofetal circulation perfusion and achieving a maternal hemodynamic stability (23) and compare it to the current NICE (National Institute for Health and Care Excellence) guidelines that are currently used, that recommends conservative management of mild pre-eclampsia through control of maternal blood pressure and frequent screening of maternal laboratory investigations' abnormalities to detect possible progression to severe pre-eclamptic toxemia (NICE guidelines 2010 [CG107]).

Aim of the work

- Aim of our study is to investigate if the use of sildenafil citrate in cases with mild pre-eclampsia is useful in pregnancy prolongation through prevention of its progression to severe pre-eclampsia and improved maternal and perinatal outcomes or not.

Subjects and methods

Study design

- Double blinded, randomized, placebo-controlled trial.

Settings and locations

- Obstetrics and Gynecology Department, Woman Health Hospital, Assiut University, Egypt.

Eligible Participants:

Inclusion criteria

- 1- Uncomplicated mild pre-eclampsia; No clinical or investigatory findings suggestive severe pre-eclamptic toxemia.
- 2- Gestational age of 28 – 36 weeks by good dates according to ACOG's – committee on obstetric practice – Method for Estimating Due Date (2014) who will receive the study's drug for at least one week before termination. (23)
- 3- Singleton viable pregnancy.
- 4- Age: 18-35 years.

Exclusion criteria

- 1- Severe pre-eclamptic toxemia (according to the NICE guidelines (2010): Hypertension in pregnancy: diagnosis and management)
- 2- Intrauterine growth retardation (23) (24).
- 3- Use of medication that could interact with sildenafil citrate such as nitrates erythromycin, ketoconazole, itraconazole, antiretroviral agents and others.
- 4- Presence of maternal co-morbidity disease as: DM, chronic hypertension, congestive heart failure, chronic kidney disease and SLE.
- 5- Placenta previa.
- 6- The patient is using aspirin.
- 7- The presence of a contraindication to the use of sildenafil citrate:
 - Hypersensitivity to sildenafil citrate or any of the tablet ingredients.
 - Patients with severe cardiovascular disease such as established cardiac failure and unstable angina pectoris.

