- Investigations:
 - Complete blood count: Hemoglobin level, white blood cells' count, platelets' count and blood film.
 - Coagulation profile: Prothrombin time and concentration and INR.
 - Screening for gestational DM.
 - Kidney function tests: Blood urea and serum Creatinine.
 - Serum uric acid.
 - Liver function tests: AST, ALT, serum bilirubin (total, direct and indirect), serum total protein and albumin.
 - Urine analysis and 24- hour's urine collection for: 24-hours protein collection in urine, urine output in 24-hours and creatinine clearance.

Randomization

- The patients will randomly allocated to either the control group or intervention group using computer generated random number tables and opaque sealed envelopes containing the patients' group allocation. The envelopes will be prepared and sent to an assigned nurse, who opens each envelope when a patient – who meets the criteria of the study- comes. All patients will be blinded to the allocation to avoid bias.
- The patients will be divided into a red group and a blue group where the intervention group would not be known by the clinician. (double-blinded)
- The intervention group will be supplied with Sildenafil Citrate (Respasio® 20mg tablets manufactured by Pharma Right Group , Egypt) according to the patient's weight by the rate of (1.5 mg/kg/day) divided into three doses per day (every 8 hours) (25-28). While the control group will be supplied with a placebo drug that has the same shape, size and color but without the active ingredient and it would also be taken in a similar way. The placebo tablet will be manufactured at the faculty of pharmacy, Assiut University.
- The patients of each group would stay in the hospital for 48 hours after the beginning of the medication for blood pressure monitoring (4 times per day) and to record any side effects detected from the medication taken.

Follow up visits:

- 1) The patients would be followed up at the obstetric outpatient clinic every 2 weeks till delivery. (According to the NICE guidelines “Hypertension in pregnancy” (2010) and the NICE guidelines “Antenatal care” (2008))

2) The follow up visits will include:

- Blood pressure measurement and review the patient's blood pressure measurements in the past 2 weeks (the blood pressure would be measured 3 times a week in any easily accessible facility to the patient).
- Urine dipstick analysis.
- Complete blood count.
- Serum creatinine & blood urea.
- AST & ALT.
- Serum uric acid.

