- Obstetric ultrasound and doppler ultrasound.

- Compliance to treatment will be ensured by checking the remainder of the medication strip.

Termination of pregnancy:

- If the patient developed any sign or investigatory/laboratory finding that represent severe pre-eclamptic toxemia:
 - 1) Persistent elevated blood pressure more than 160/110 mmHg.
 - 2) HELLP syndrome.
 - 3) Eclampsia.
 - 4) Intrauterine fetal death.
 - 5) Abrupt body swelling.
 - 6) Severe headache, epigastric pain and/or right hypochondrial tenderness.
 - 7) Elevated liver enzymes: ALT or AST rising to above 70 iu/litre.
 - 8) Platelet count falling to below 100×10^9 per litre.

9) Serum creatinine >125 mmol/litre (29).

- If no complications occurred and the maternal blood pressure is controlled on the medication , termination would be after completion of 36 weeks and 6 days as recommended by the NICE guidelines (2010) : “Hypertension in pregnancy : Diagnosis and management”

Primary outcome

Gestational age at time of termination and maternal outcome in terms of whether the disease would progress to severe pre-eclampsia or not.

[figure not shown]
Secondary outcomes

- 1- Neonatal outcome in terms of survival and neonatal well-being (by obtaining the birth weight and the apgar score at 1 and 5 minutes and direct postnatal need to NICU).
- 2- Control of maternal blood pressure.
- 3- Method of termination of pregnancy.
- 4- Identification of possible maternal side effects from the use of sildenafil citrate i.e.; headache, flushing and dyspepsia.
- 5- Evaluation of the effect of sildenafil citrate on the feto-maternal circulation through the Doppler ultrasound.

Final status:

- We will specify the number of patients who were candidates for the study ,the number of patients who were excluded for not meeting the criteria ,the number of patients who were included the study, the number of patients who were excluded for lack compliance to treatment or dropped follow-up visits and the number of patients who successfully completed the study till delivery.

THE TRIAL FLOW CHART

Approval of Ethical Considerations

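### Outside blood pressure readings and laboratory tests are reviewed at 2-weekly visits with no onset date recorded, so up to 14 days of silent severe disease can count as gestation in the primary outcome

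*Combined protocol and SAP*

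**What the plan says.** All provisions are in the combined protocol and SAP.

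- **Follow up visits, item 1:** "The patients would be followed up at the obstetric outpatient clinic every 2 weeks till delivery".
- **Follow up visits, item 2:** each visit includes a review of "blood pressure measurements in the past 2 weeks (the blood pressure would be measured 3 times a week in any easily accessible facility"). Blood count, creatinine, liver enzymes and dipstick are listed in the same visit schedule. No other review point or reporting route is given.
- **Randomization, last item:** each patient "would stay in the hospital for 48 hours after the beginning of the medication for blood pressure monitoring (4 times per day"). This is the only period of close observation.
- **Termination of pregnancy:** a sign or finding of severe disease triggers termination. Item 1 is "Persistent elevated blood pressure more than 160/110 mmHg"; persistence is not defined. Items 7 to 9 are laboratory results. Items 3, 5 and 6 (seizure, sudden swelling, head or upper abdominal symptoms) can come to light at any time.
- **Primary outcome:** "Gestational age at time of termination and maternal outcome in terms of whether the disease would progress to severe pre-eclampsia or not". No date of onset of severe disease is defined.
- **Statistical Analysis:** t-test and chi-square only.

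**The concern.** Gestational age at termination stands in for how long the disease stayed mild. For a woman who progresses, it is the sum of the time until a severe feature appears and the time until someone who can act learns of it. The aim of the trial concerns the first part. The follow-up schedule adds the second, and nothing is recorded that would separate them.

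A woman with repeated readings above the item 1 limit and no symptoms, or with a laboratory abnormality alone, may have no scheduled contact with the trial team until her next visit. Her pregnancy is then recorded as longer because the finding was late.

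Two things are at stake. One is whether a difference between arms, or its absence, can be read as an effect on disease. The other is safety: the termination rule acts once a severe feature develops, yet the schedule provides for looking at the relevant readings in retrospect.

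**Working it through.** **1. The plan's own figure.** Sample size gives alpha 5%, power 95% and 40 per group, with no effect size, SD or progression rate, so the 80 cannot be reproduced. Inverting the two-mean formula (two-sided, assumed because sidedness is not stated):

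d = (1.960 + 1.645) × √(2/40) = 0.806 SD. One-sided it would be 0.736 SD.

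**2. Length of the delay.** Input from Follow up visits: a 14-day interval. Assumption: onset is uniform between visits. For silent progression:

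- maximum 14 days
- mean 14/2 = 7 days
- SD 14/√12 = 4.04 days

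**3. Effect on the comparison if the delay is the same in both arms.** Let pC and pT be the progression rates on placebo and sildenafil, and s the share of progression that is silent. The mean added gestation is 7·s·p in each arm, so a true benefit shrinks by 7·s·(pC − pT). The documents give none of these rates; all are assumed.

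- 40% vs 20%, s = 1: 2.8 days added on placebo and 1.4 on sildenafil; benefit shrinks by 1.4 days.
- The same rates, s = 0.5: 7 × 0.5 × 0.20 = 0.7 day.
- Rate difference 0.10 to 0.40, s = 1: 0.7 to 2.8 days.
- Equal rates: 0.

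**4. Cost in power.** Suppose the trial had exactly 95% power for gestational age without the delay. Then power = Φ[(Δ − loss)/(SD × √(2/40)) − 1.960], with Δ = 0.806 × SD and s = 1. The SDs are assumed, and the extra spread from the delay is ignored.

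| SD (days) | Δ (days) | loss 0.7 | loss 1.4 | loss 2.8 |
|---|---|---|---|---|
| 10.5 | 8.46 | 91% | 85% | 67% |
| 14 | 11.28 | 92% | 88% | 77% |
| 21 | 16.93 | 93% | 91% | 85% |

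**5. If the arms differ in how progression is found.** With equal progression p and silent shares that differ by δ, the arm means shift by 7·p·δ with no difference in disease. For δ = 0.20 this is 7 × 0.20 × 0.20 = 0.28 day at p = 20%, and 7 × 0.40 × 0.20 = 0.56 day at p = 40%. For δ = 0.50 at p = 40% it is 1.4 days. The sign of δ is not known, so each figure can go either way.

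**6. What the planned readings could recover.** If onset by blood pressure is dated from the outside readings themselves (gaps of 2, 2 and 3 days assumed), the mean dating error is (2² + 2² + 3²)/(2 × 7) = 17/14 = 1.2 days, and the maximum is 3. This leaves aside how many readings make an elevation persistent. Laboratory-only onset remains known only to within the 14-day interval.

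**The case against.** Several objections are sound and limit the point.

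- **Review at visits is inferred from silence.** The protocol says what visits include; it does not forbid a facility or the patient from reporting earlier. The patient information and consent pages are not in the available text and might carry such an instruction. This stands, so the point is that no route is stated, not that none exists.
- **Not all progression waits for a visit.** Symptoms can surface at any time, the first 48 hours are in hospital, and planned termination after 36 weeks and 6 days limits the delay in late enrolments. The 14-day figure is an upper bound for silent progression.
- **A reader might infer that one very high reading already meets the termination rule and is ignored.** It does not: item 1 requires persistence. The case of concern is repeated high readings.
- **A reader might infer that the delay favours sildenafil.** The documents do not support this. Both arms follow one blinded schedule, and a common delay adds more days to the arm with more progression, so it works against a true benefit. It might be argued that a vasodilator would mask pressure and leave laboratory tests to reveal progression. But under this schedule outside pressures and laboratory results wait for the same visit. Only symptoms break the pattern, and there headache and dyspepsia, listed under Secondary outcomes as possible side effects, overlap with the symptom triggers and could bring sildenafil terminations forward.
- **A reader might infer a contradiction with the introduction,** which describes the comparator as frequent laboratory screening "to detect possible progression to severe pre-eclamptic toxemia". The introduction gives no interval, and Follow up visits attributes its schedule to the same body's guidance, so no contradiction can be shown.
- **The yes/no component is largely spared.** Progression found at the next visit is still counted; its date is what moves.

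None of this removes the core: followed as written, the schedule lets unseen days enter gestational age, and nothing recorded allows them to be separated out.

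**Conclusion.** The point holds in this limited form. Silent progression can go unseen for up to 14 days, with a mean of about 7 under uniform onset, and those days count as gestation because no onset date is recorded. The 14-day bound follows from the schedule if visits are kept and no unstated route operates.

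The effect on the comparison rests on assumed rates. Dilution is about 1.4 days at 40% versus 20% progression if all progression is silent, less if only part of it is, and zero if rates are equal. A bias from different modes of detection is possible in either direction and cannot be sized from the documents. The plan should be changed on this point, both for interpretation and because the retrospective review does not sit with a termination rule triggered when a severe feature develops.

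**What to change.** 1. **Record onset separately.** Capture the date of the first reading, symptom or laboratory result that meets a criterion under Termination of pregnancy, and how it was found (outside reading, symptom, scheduled visit), apart from the termination date. For item 1, the protocol must say what persistence means and which reading dates it; that definition is for the clinical team.
2. **Report it.** Present time from randomisation to that date by arm beside gestational age at termination, and tabulate mode of detection by arm. Women terminated without a qualifying finding are censored at termination, so a time-to-event summary is needed in addition to the planned tests.
3. **Reconcile the text.** Bring the retrospective review under Follow up visits into line with the termination trigger. The clinical team should settle how and when outside readings reach the blinded clinician. State also whether the measurement technique under Preliminary assessment of patient applies to readings that decide the outcome.

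The cost is a few data fields, one extra analysis and a short protocol paragraph; the readings are already planned. Recorded onset will precede termination, so apparent prolongation may look smaller. Laboratory-only onset will still be known only to within the visit interval.

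### Severe headache alone can trigger termination while headache is also a listed sildenafil effect; the trigger is not visibly recorded, and one colour per arm means one correct guess exposes a whole arm

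*Combined protocol and SAP*

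**What the plan says.** Under Termination of pregnancy, the list opens with "If the patient developed any sign or investigatory/laboratory finding that represent severe pre-eclamptic toxemia". Item 6 of that list is "Severe headache, epigastric pain and/or right hypochondrial tenderness". The item asks for no accompanying blood pressure or laboratory finding.

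The primary outcome is "Gestational age at time of termination and maternal outcome in terms of whether the disease would progress to severe pre-eclampsia or not". Secondary outcome 4 is "Identification of possible maternal side effects from the use of sildenafil citrate i.e.; headache, flushing and dyspepsia".

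Under Randomization, the tablets are matched for shape, size and colour, and "The patients will be divided into a red group and a blue group where the intervention group would not be known by the clinician". Women stay in hospital for 48 hours after starting treatment, with side effects recorded, and then continue as outpatients. Under Follow up visits, blood pressure is taken three times a week and reviewed at two-weekly visits. The blood tests and urine dipstick are done at those visits.

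The counts promised under Final status cover screening, exclusion, drop-out and completion. They do not include the reason for termination.

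**The concern.** One symptom appears in two roles. Severe headache is a reason to end the pregnancy as severe disease, and headache is a possible effect of the study drug. A drug-related severe headache acted on under item 6 would set gestational age at termination directly. If the termination list also defines progression, it would count as a progression event too. Both primary outcomes would then move against sildenafil. This route cannot create a false benefit.

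Without a record of the trigger, nobody could say afterwards how many events arose this way. The regular blood pressure and laboratory results would identify some symptom-only cases by exclusion, but not all of them.

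The colour code is a separate route to the same judgement. Suppose someone correctly infers one woman's treatment, for example from flushing. Every other woman with that colour is then identified to anyone who sees the colours. A headache could be dismissed as a drug effect or read as disease accordingly, so this bias could go either way.

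**Working it through.** **Reading the passages together.** Any one listed finding suffices, and item 6 stands alone. The lead-in requires the finding to represent severe disease, which leaves room to set aside a symptom judged to be a drug effect, but no rule for that judgement is visible. The natural reading is that the same list defines progression. The background and exclusion criterion 1, however, refer to the NICE guideline, and the visible text does not say which source governs the outcome. The direct overlap is severe headache only. Dyspepsia against epigastric pain is an inference, and no overlap is claimed for right hypochondrial tenderness.

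**The plan's own figure.** Sample size gives alpha 5%, power 95% and 40 per group, but no event rates, effect size or SD. It cannot be reproduced or tied to progression. The pair 40% v 7% is used below only because 40 per arm gives it about 95% power (95.1% by the normal approximation, 96.3% exact).

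**Model.** Let p be the true progression rate and q the share of non-progressing women terminated on a symptom alone. The observed rate is p + (1 − p)q. All values of p and q are assumptions. The test is Pearson chi-square without continuity correction, two-sided 0.05, 40 per arm, with exact binomial probabilities.

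Example: p = 20%, q = 10% on sildenafil gives 0.20 + 0.80 × 0.10 = 0.28, compared with 0.20 on placebo.

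**False rejection with no true effect:**

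| True progression, both arms | Baseline | q = 5%, none on placebo | q = 10%, none on placebo | q = 5%, half on placebo | q = 10%, half on placebo |
|---|---|---|---|---|---|
| 20% | 5.1% | 7.2% | 13.3% | 5.6% | 6.9% |
| 30% | 4.8% | 6.1% | 9.8% | 5.1% | 6.1% |
| 50% | 5.7% | 6.3% | 8.1% | 5.8% | 6.2% |

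**Power, true 40% v 7% (96% without the problem).** With q = 10%, the observed sildenafil rate is 0.07 + 0.93 × 0.10 = 0.163. The excess is 0.093 × 40 = 3.7 women.

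| Sildenafil q | None on placebo | Half the rate on placebo | Same rate in both arms |
|---|---|---|---|
| 5% | 85% | 88% | 91% |
| 10% | 67% | 76% | 83% |

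The half-rate column includes dilution. For 10% v 5%, a shared 5% alone takes power from 96% to 91%; only the further fall to 76% comes from the imbalance.

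**Gestational age.** The fall in the arm mean is the share affected times the weeks lost. If 5% to 10% of sildenafil women were delivered 1 to 4 weeks earlier, the mean would fall by 0.05 × 1 = 0.05 weeks to 0.10 × 4 = 0.4 weeks (0.35 to 2.8 days). No power figure is attached, because the plan gives no SD and the distribution has a planned end point ("termination would be after completion of 36 weeks and 6 days" for uncomplicated cases).

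**How far recoding can mislead.** Take 50% true progression in both arms. Suppose 10% of the sildenafil women who would have progressed are terminated on headache first and are then recoded as not progressed. The observed sildenafil rate is 0.50 × 0.90 = 0.45. Rejection is 8.1%, of which 7.2 percentage points favour sildenafil.

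**The case against.** The case against has several sound parts.

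- **Severity.** Item 6 requires severe headache; the side-effect list says only headache. No visible text says sildenafil causes severe headache, and the background hopes this drug class will avoid the headaches seen with nitric oxide. This limits the overlap but does not remove it, since headache remains a listed effect and severity is not defined.
- **Monitoring.** A reader might infer that nothing is measured between two-weekly visits. In fact blood pressure is taken three times a week, so symptom-only cases could be partly identified later. Laboratory findings between visits would still be missing.
- **Side-effect capture.** It would be wrong to say that side effects matter only in the first 48 hours, because secondary outcome 4 has no such limit. Recording a headache is still not the same as recording it as the reason for termination.
- **Missing material.** A trigger field could sit in a case record form or in the figure or flow chart, none of which could be read. The statement is therefore limited to the visible text.
- **Size.** Alarming figures are available: 20% symptom-only terminations on sildenafil, none on placebo and 20% progression give 35.5% false rejection. Nothing in the documents supports such rates, nor a zero rate on placebo in women who have pre-eclampsia.
- **Blinding.** A reader might infer that the colour code unblinds the trial. The tablets are matched, clinicians are stated to be unaware of which group is active, and the text does not say that they see the colours.

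**Conclusion.** The point holds as a conditional risk that is cheap to remove. If sildenafil causes some severe headaches, some drug effects could be counted as progression and could bring termination forward, biasing both primary outcomes against sildenafil. The documents do not support saying that this will happen, or that it could make sildenafil look better.

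The size is unknown. On the assumed 5% to 10% rates, false rejection rises modestly, to 6.1% to 13.3% with none on placebo, and hardly at all (5.1% to 6.9%) with half the rate on placebo. The loss of power for 40% v 7% is more noticeable: to 85% and 67% with none on placebo, or 88% and 76% with half the rate, part of which is dilution. These figures also assume that item 6 terminations count as progression, which is the natural reading but is not stated.

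The colour code is a separate risk of unknown size that could act in either direction. Together these justify a recommended change, with medium confidence; neither invalidates the design.

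**What to change.** 1. Under Randomization, replace the red and blue group code with a unique treatment code for each woman. Someone not involved in care or outcome assessment holds the list. This stops one inference from spreading to the whole arm; it does not prevent a guess about one woman.
2. Record the item or items on the termination list that triggered each termination. Tabulate headache-only terminations and other item-6-only terminations by arm.
3. Keep the planned primary analysis. Pre-specify one sensitivity analysis of progression in which headache-only terminations, with no other listed item met, are recoded as not progressed in both arms. Label it as a bound, because it can favour sildenafil. Do not recode all item 6 terminations: that would also remove right hypochondrial tenderness. Describe gestational age for the headache-only women by arm.

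The clinical termination rule is unchanged. The cost is slightly more labelling and packing work, one case-record field, one table and one extra analysis. The sensitivity analysis carries its own possible bias, so it cannot replace the primary result.
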